3.6 Patients who are registered for tissue acquisition only

Due to the rare nature of SBA we would like to collect some information on patients who are unwilling or unable to consent for the randomised trial. All patients who have R0 resected SBA with no evidence of metastasis at the time of signing consent are eligible for tissue acquisition only. This will involve the patient signing a separate registration consent form and include the collection of demographic, clinic-pathological, epidemiological and survival data. Patients who consent to registration must be registered via the telephone number above within 28 days of signing consent. In addition archival FFPE and a blood sample will be collected for these patients to allow molecular profiling and future translational research. A questionnaire about underlying risk factors (e.g. Crohn's disease, coelic disease, Lynch Syndrome etc.) will be completed also. The patients should ideally be registered and have venous blood sampling before starting adjuvant chemotherapy, but this may also be done afterwards as long as the patient has no evidence of progression at the time of sampling.

Patients who are entering the registration only part of the study should be consented using patient information sheet D.

3.7 Withdrawal

Patients have the right to withdraw for the trial at any point for any reason and investigators have the right to withdraw a patient from treatment for medical concerns. When a patient expresses a wish to withdraw it is important to determine and record whether the patient wants to stop trial treatment only or to withdraw from the trial as a whole.

3.7.1 Withdrawal of Patients from Trial Treatment

Patients have the right to withdraw from trial treatment at any point for any reason. Similarly the investigator may withdraw patients from the trial drug in the event of intra-current illness, adverse events, serious adverse events, SUSARs, protocol violations or any other relevant reasons. If a patient withdraws from treatment early they should be followed up as per trial schedule.

Version 6: 16th July 2021 Page 30 of 87

3.7.2 Withdrawal from Trial

The patient can decide to withdraw their consent from the trial at any time. If the patient wants to withdraw consent for the trial, then a Consent Withdrawal Form should be completed by the site and sent to the CRUK Glasgow CTU. Once a patient has withdrawn from the trial no further data will be collected on that patient and no further samples collected. It should be clearly documented in the patient's notes and the Consent Withdrawal Form what the patient is withdrawing from i.e. further data being collected or the right to use data and samples collected prior to this point.

4 TRIAL DESIGN

4.1 Trial Schedule

For Group 1 patients randomised to observation only:

Clinic visits are mandated at screening, 3 months post randomisation, 6 months post randomisation, 9 months post randomisation, 12 months post randomisation then every 6 months until 3 years post randomisation and then annually for up to 7 years post randomisation.

For Group 1 patients randomised to chemotherapy and for all Group 2 patients:

Clinic visits are mandated at screening, during treatment for chemotherapy, 9 months post randomisation, 12 months post randomisation then every 6 months until 3 years post randomisation, then annually for up to 7 years post randomisation.

4.1.1 Pre-randomisation Evaluations

- Within **14 weeks** of trial entry the patient must have had surgery. The authorised pathology report must confirm microscopically clear surgical resection margins. A FFPE archival sample of tumour must be made available to the trial team for molecular profiling and further translational research. This can be sent after the patient has been randomised.
- Within **12 weeks** of trial entry a CT chest, abdomen and pelvis or CT chest and MRI abdomen and pelvis must be performed. If this is outside the required time window it must be repeated after the patient has given written informed consent for the trial.
- Within 28 days of registration/randomisation written, informed consent must be provided.
- Within **7 days** of trial entry the following must have occurred:
 - Review of eligibility criteria
 - Medical history
 - o Physical/Clinical assessment including height and weight
 - Clinical assessment of neuropathy (baseline)
 - o Clinical assessment of sensorineural hearing impairment (baseline)
 - Body Surface Area
 - ECOG performance status
 - Baseline ECG

- Haematology blood sample including coagulation profile
- Biochemistry including U&E, LFTs, magnesium and GFR
- Urine pregnancy test for all women of childbearing potential
- Baseline QoL questionnaires EQ-5D and EORTC QLQ-C30 and CR29
- o Archival blood sample for molecular profiling and future translational research
- A questionnaire about underlying risk factors (e.g. Crohn's disease, coelic disease, Lynch
 Syndrome etc.) will be completed at time of study entry

Any time prior to randomisation

DPD Deficiency test if mandated as standard of care or if clinically indicated

4.1.2 Evaluations While on Trial Treatment

Prior to each cycle of chemotherapy the following tests should be performed:

- ECOG performance status
- Toxicity Assessment (only toxicities which are grade 2 or above require entry to the CRF)
- If the patient has been randomised to receive oxaliplatin treatment clinical assessment of neuropathy should be performed at all study visits
- If the patient has been randomised to receive oxaliplatin treatment clinical assessment of sensorineural hearing impairment should be performed at all study visits
- Haematology blood sample (full blood count). From cycle 2 onwards pre-cycle bloods should be performed within 2 days of treatment. For patients on anti-coagulant therapy, appropriate clotting factors should be tested at each chemotherapy visit.
- Biochemistry including U&E, LFT, magnesium and calculated or measured GFR. From cycle 2 onwards pre-cycle biochemistry should be performed within 2 days of treatment
- QoL questionnaires when required EQ-5D and EORTC QLQ-C30 and CR29 (at 3 and 6 months post randomisation)

If a patient stops their allocated treatment early or if the patient experiences treatment delays the BALLAD UK follow-up visits will still be due as per the protocol schedule i.e. timed relative to date of randomisation. This is the required procedure even if the patient has experienced treatment delays and is still receiving chemotherapy treatment.

4.1.3 Evaluations for patients on observation only: From randomisation to 6 months

Patients who are randomised to observation will only have a visit at 3 and 6 months post randomisation. At these visits the following will be performed:

- Haematology blood sample (full blood count).
- Biochemistry including U&E, LFT, magnesium and calculated or measured GFR

Version 6: 16th July 2021 Page 32 of 87

QoL will be completed

The follow-up schedule (from 9 months post randomisation) will be the same as for those patients who are randomised to receive chemotherapy.

4.1.4 Follow up Evaluations

Patients will be followed up 9 months post randomisation and 12 months post randomisation. After that they will have visits on a six monthly basis until 3 years post randomisation and will then have

annual visits for up to 7 years post randomisation.

Follow-up CT Scanning

CT Chest Abdomen and Pelvis will be performed at approximately 12, 24 and 36 months post randomisation. (Contrast enhanced CT Chest, abdomen and pelvis is the preferred method of assessment but MRI abdomen and pelvis with non-contrast enhanced chest CT may be used instead

where clinically indicated).

Additional CT scans may also be conducted as clinically indicated based on symptoms, clinical markers

or to accommodate sites usual scanning regimen.

CT scans performed within 42 days of the follow-up visits may be used for disease assessment. If the

time interval from CT to follow up visit is more than 42 days a new CT scan should be performed.

If a patient has reached the primary endpoint of the trial and has a recurrence or a new primary tumour

(CT confirmed) then further protocol mandated CT scans are no longer required. Any post recurrence

CT scans should be performed as per local practice at the discretion of the investigator. The results of any further scans should be recorded in the appropriate section of the Case Report Form (CRF) unless

the patient has commenced further palliative systemic therapy.

Follow-up Quality of Life Assessments

Please see the schedule of assessment for collection time-points during treatment (baseline, 3 and 6

months post randomisation).

EORTC QLQ-C30 and CR29 will be completed at 9, 12, 18 and 24 months post randomisation for all

arms of the trial.

The EQ-5D will be completed at 9, 12, 18, 24, 30, 36, 48, 60 72 and 84 months post randomisation

for all arms of the trial.

For patients that have a recurrence or have a new primary tumour the quality of life questionnaires

should continue to be completed as per schedule of assessments provided it is deemed appropriate to

ask the patient to do so.

Resource use for health economic assessment

Version 6: 16th July 2021 Page 33 of 87

Resource use data collection for the health economic assessment will be limited to health service resource use in the secondary care setting. Data (hospital inpatient, outpatient and day cases, cytotoxic drug use at relapse) will be collected on the treatment and follow-up forms.

4.2 Translational Research

Funding has been secured to support the collection of FFPE blocks and bloods for patients on the BALLAD UK trial. The aim of collecting this material is to establish a large biobank of SBA tissue and blood with complete and comprehensive trial quality follow-up data which will act as the foundation for many future collaborative research projects and for combined projects with other funded tissue collections. Expected research projects arising will include definition of new prognostic markers in this group of patients and definition of pharmacogenetic markers of 5-FU/capecitabine and oxaliplatin toxicity, particularly high grade diarrhoea and neurotoxicity.

This is a hugely important and integral part of the BALLAD UK trial that will significantly enhance the potential impact and clinical applicability of the results of the main body of the trial. We are therefore keen that all researchers contribute as much as possible to this part of the trial and encourage their patients to give their consent to allow this to take place.

Tumour Specimens:

We plan to collect the paraffin embedded tumour tissue which will have been obtained at surgical resection of patient's primary tumour prior to entry into BALLAD UK.

Blood samples:

We will collect blood samples – a 5ml serum sample and 2 x 9ml EDTA samples (for DNA) from each patient who consents to this. **If possible we would prefer it if these bloods could be taken prior to starting the adjuvant therapy**. However, it would still be useful to receive these bloods taken at any point during the treatment or follow-up period and there is still very useful translational research that we can carry out on these samples whatever the time-point at which they are collected. Therefore please do send samples from any patient who consents to give their blood for this research (and are not known to have had disease progression at the time of sampling).

Sample collection, storage and processing:

Further detailed instructions for the processing, labelling, handling storage and shipment of these specimens will be provided by in a separate BALLAD laboratory manual.

Proposals for specific translational research projects utilising the material will be considered by the Trial Management Group and presented to the Umbrella Trial Steering Committee for approval.

Version 6: 16th July 2021 Page 34 of 87

4.3 Trial Endpoints

4.3.1 Primary Endpoints

Disease free survival is the primary end point for the trial. This is defined at time from randomisation to the first occurrence of the following events:

Disease relapse (confirmed by imaging)

Incidence of a new primary (confirmed by imaging and histology/cytology)

Death from any cause

Patients who experience none of these events are censored at the last date known to be alive.

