An open-label, randomised, controlled, multi-centre, trial with disease free survival as the primary endpoint. Data from BALLAD UK will be pooled with data generated from a number of different, individual, parallel prospective studies addressing the same objectives with similar designs brought together under the framework of the International Rare Cancer Initiative. This worldwide data collaboration is referred to as GLOBAL BALLAD. This protocol is for BALLAD UK, which is the component of GLOBAL BALLAD led from the UK. Other countries contributing data to GLOBAL BALLAD will develop their own protocol and put in place their own sponsorship arrangements and be responsible for trial management and safety reporting for the trials they develop.

Objectives:

- 1. Assessment of the efficacy of observation versus 24 weeks of adjuvant post-operative chemotherapy in resected stage I-IV small bowel adenocarcinoma (SBA).
- 2. Assessment of the efficacy of 24 weeks of adjuvant post-operative fluoropyrimidine 'monotherapy' regimen versus fluoropyrimidine plus Oxaliplatin combination chemotherapy regimen in resected stage I-IV small bowel adenocarcinoma (SBA).

Endpoints:

Primary Endpoint

Disease free survival (defined as time from randomisation to recurrence, development of new primary or death from any cause).

Secondary Endpoints

Overall survival, cost-effectiveness, toxicity, clinico-pathological, epidemiological and molecular profiling of SBA.

Population:

Patients with SBA that has been potentially cured surgically.

Eligibility:

Inclusion Criteria

- 1. R0 resected stage I, II, III or IV SBA
- 2. No evidence of residual or metastatic disease at laparotomy or on CT/MRI imaging of chest, abdomen and pelvis.
- 3. Patients must be registered and randomised within 14 weeks of surgery and commence chemotherapy within 16 weeks of surgery
- 4. ECOG Performance Status of 0 or 1
- 5. Absolute neutrophil account $\geq 1.5 \times 10^9/I$

Version 6: 16th July 2021 Page 7 of 87

- 6. Platelet count $\geq 100 \times 10^9/l$
- 7. Haemoglobin ≥90 g/l (previous transfusion is allowed)
- 8. AST and ALT \leq 2.5 x upper limit of normal (ULN). (At least one of ALT or AST MUST be performed)
- Creatinine clearance > 50 ml/min (calculated by Cockcroft Gault or Wright equation) or measured by EDTA
- 10. Serum bilirubin ≤ 1.5 x ULN
- 11. Signed and dated informed consent indicating that the patient has been informed of all the pertinent aspects of the trial prior to enrolment.

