1 INTRODUCTION

1.1 Background

Small bowel adenocarcinoma (SBA) is a rare cancer, representing less than 5% of gastrointestinal cancers, with approximately 2,000 new cases of SBA and 1,100 deaths from this in the United States in 2008 (1, 2). 60-70% of SBA cancers are potentially curable (i.e. stages I – III). The annual incidence of SBA is about 2.2 - 5.7 per million inhabitants in Western countries. The incidence of SBA is increasing, particularly those with a duodenal location. The incidence of SBA is higher in industrialised countries, increases with age, and is more frequent in males than females. Those of Afro-Caribbean descent have a significantly higher incidence rate than other racial groups. Adenocarcinomas are mostly distributed proximally in the small intestine, with approximately 45% within the duodenum, 35% in the jejunum and 20% in the ileum. One of the most important known risk factors in the pathogenesis of SBA is previous Crohn's disease. The risk for developing SBA is increased in patients with coeliac disease (relative risk, 60- to 80-fold) but the mechanisms that predispose coeliac disease patients to SBA are not known. SBA is also associated with Familial Adenomatous Polyposis (FAP), Peutz-Jeghers syndrome, hereditary non-polyposis colorectal cancer (Lynch syndrome), cystic fibrosis and peptic ulceration. Behavioural risk factors include consumption of red meat, smoked and salt-cured foods and saturated fat, obesity and smoking

The clinical presentation and diagnosis of SBA is usually delayed, with an average delay of six to eight months from onset of symptoms. This is primarily because small bowel tumours are not accessible by endoscopic examination, especially when they are distal to the second part of the duodenum. Because of the non-specific nature of presenting clinical manifestations and the lack of effective tools for exploring the small bowel, SBA is usually diagnosed at an advanced stage. Most commonly, patients present with signs and symptoms of obstruction, though anaemia with haemoccult-positive stools is also a frequent occurrence. SBA can be diagnosed through an upper GI or small intestine oral contrast follow-through study or CT scan. Recently, capsule endoscopy has been used in the diagnosis of such tumours. Histological confirmation can be obtained via an upper gastrointestinal endoscopy, with total duodenoscopy in duodenal lesions, but the diagnosis remains obscure for most distal lesions until laparotomy.

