5.8 Concomitant Therapies

Surgery

Surgery is allowed during the trial for adhesive or other obstruction, intercurrent other disease or for any other clinically appropriate reason. Continuation of adjuvant chemotherapy after a break where appropriate may be permitted following discussion with the CI or his approved representative through the Glasgow CRUK Clinical Trials Unit.

Radiotherapy

Radiotherapy is not permitted during the trial.

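### As Protocol 4.3.1 is written, a relapse or new primary proven by tissue but not imaged is not a DFS event, and three sections disagree on what confirmation is needed

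*Protocol*

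**What the plan says.** The primary endpoint is described in three places.

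- **Trial summary, Endpoints:** "Disease free survival (defined as time from randomisation to recurrence, development of new primary or death from any cause". No confirmation is required for any component.
- **Protocol 4.3.1:** the first of three events. For relapse: "Disease relapse (confirmed by imaging". For a new primary: "Incidence of a new primary (confirmed by imaging and histology/cytology". The third, "Death from any cause", carries no condition. Everyone else falls under the censoring rule: "Patients who experience none of these events are censored at the last date known to be alive".
- **Protocol 4.1.4:** once the primary endpoint has been reached with a recurrence or new primary, the text continues "CT confirmed) then further protocol mandated CT scans are no longer required". One imaging condition covers both kinds of event, and histology is not mentioned.

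Protocol 4.1.4 schedules CT at about 12, 24 and 36 months and allows further CT when clinically indicated. Follow-up runs to 7 years.

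**The concern.** Histology is normally the firmer proof of malignancy. Yet under 4.3.1 it does not confirm a relapse at all, and for a new primary it is not enough without imaging. Disease can come to light by tissue first. Protocol 5.8 foresees operations on trial patients ("Surgery is allowed during the trial for adhesive or other obstruction, intercurrent other disease or for any other clinically appropriate reason"), and Protocol 1.1 notes that most distal small-bowel lesions stay undiagnosed until laparotomy. A patient with tissue-proven but unimaged disease would, on the literal rule, go on accruing disease-free time while known to have cancer.

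The second problem is the disagreement between sections. The same patient can be an event under one section and event-free under another. In an open-label trial whose data are pooled across national studies, that invites different coding by site and by country. What is at stake is mainly the validity and consistency of the primary endpoint. Loss of power is secondary.

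**Working it through.** **Step 1: apply each section to the same cases.**

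| Case | Summary | 4.1.4 (CT-confirmed) | 4.3.1 |
|---|---|---|---|
| Relapse seen on CT | event | endpoint reached | event |
| Relapse proven by tissue, not imaged | event | not met | **not an event** |
| New primary on CT and by tissue | event | endpoint reached | event |
| New primary on CT, no tissue | event | can be read as reached; mandated CT ends | **not an event** |
| New primary proven by tissue, not imaged | event | not met | **not an event** |

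The sections agree only in rows one and three. In the second and fifth rows the censoring rule of 4.3.1 keeps the patient event-free until a scan shows the disease or the patient dies. If neither happens, the patient is censored at the last date known to be alive. After month 36 no scheduled scan remains that could turn such a case into an event.

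**Step 2: reproduce the stated power.** Inputs from Protocol 7.2: hazard ratio 0.775, one-sided alpha 0.20, and projected events d = 68 (Question 1) and 98 (Question 2). Allocation is 1:1 (Protocol 3.5). With the Schoenfeld formula,

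Power = Φ(√(d/4) × |ln 0.775| − z₀.₈₀), where |ln 0.775| = 0.2549 and z₀.₈₀ = 0.8416.

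- Question 1: √(68/4) = 4.123; 4.123 × 0.2549 − 0.8416 = 0.209; Φ = 58.3%. The protocol states 58%.
- Question 2: √(98/4) = 4.950; 4.950 × 0.2549 − 0.8416 = 0.420; Φ = 66.3%. The protocol states 66%.

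Both reproduce. No stated figure is wrong because of the definition.

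**Step 3: remove a share of events.** The documents give no rate of tissue-proven, unimaged events, so the share is an assumption and is shown as a range. Every affected event is treated as lost for good, which is pessimistic.

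| Share lost (assumed) | Q1 events | Q1 power | Q2 events | Q2 power |
|---|---|---|---|---|
| 0% | 68 | 58.3% | 98 | 66.3% |
| 2% | 66.6 | 57.9% | 96.0 | 65.8% |
| 5% | 64.6 | 57.2% | 93.1 | 65.1% |
| 10% | 61.2 | 56.2% | 88.2 | 63.9% |
| 15% | 57.8 | 55.1% | 83.3 | 62.6% |

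At 10% the loss is 58.3 − 56.2 = 2.1 points for Question 1 and 66.3 − 63.9 = 2.4 points for Question 2.

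**Step 4: allow for the UK share.** The 68 and 98 events are pooled GLOBAL BALLAD projections. The recruitment figure labels in 7.2 show 10 UK patients among 77 for Question 1, or 13%. If events split in the same way and only the UK protocol carries this wording (both assumptions), about 0.13 × 68 = 8.8 events are affected by it, and 10% of those is about 0.9 of an event. Power at 67.1 events is Φ(√(67.1/4) × 0.2549 − 0.8416) = Φ(0.202) = 58.0%, a change of 0.3 points.

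**The case against.** The strongest reply is that the rule will rarely matter. A patient with biopsy-proven cancer will usually be scanned soon, and the schedule notes and 4.1.4 allow additional CT when clinically indicated. Protocol 1.2 reports distant relapse in 81–100% of recurrences, a pattern that chest, abdomen and pelvis imaging is meant to find. Death counts without any condition. Requiring imaging is also a uniform, objective criterion for an open-label trial, and the summary is an abbreviated statement, so its silence need not be a rival rule. All of this stands as an argument about size.

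On 4.1.4 it can be added that the sentence asks both that the endpoint has been reached and that the finding is CT-confirmed, so a careful site would not stop scans on CT alone. That reading is possible. But the only confirmation named there is CT, so the opposite reading is just as natural, and the section does not settle it.

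A reader might infer that biopsy-proven events in general are dropped, or are dated up to 12 months late at the next annual scan. The documents do not support that. Only events without prompt imaging are exposed, and the protocol states no event-dating rule. Such a rule may properly sit in an analysis plan that is not shown. A reader might also infer that the trial population carries polyposis or Lynch syndrome. Protocol 1.1 says only "SBA is also associated with Familial Adenomatous Polyposis (FAP), Peutz-Jeghers syndrome, hereditary non-polyposis colorectal cancer (Lynch syndrome" and gives no prevalence.

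What the reply does not remove is the rule itself. What counts as an event is fixed in the protocol, and extra CT is optional, so whether a proven event counts can depend on local discretion.

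**Conclusion.** The point holds as a defect of definition with a small expected effect. On the text of 4.3.1, a relapse or new primary proven by tissue but not imaged is not a DFS event, and the summary, 4.1.4 and 4.3.1 set three different standards of confirmation.

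The cost in power is about 2 points for each question if 10% of pooled events were lost, and about 0.3 points for Question 1 if only UK events are affected in proportion to UK recruitment. The 10% and the UK share of events are assumptions, and so is the treatment of affected events as permanently lost. A claim of material power loss would go beyond the documents. The reason to act is that the correction reduces misclassification of the primary endpoint, and makes coding consistent across the pooled trials, without any extra procedure.

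**What to change.** In 4.3.1, define the two events along these lines:

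- *Relapse: shown by imaging, by histology/cytology, or by both.*
- *New invasive primary: proven by histology/cytology, with or without imaging.*

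Dropping the imaging condition would also let in tumours that it now tends to keep out. The text should therefore say whether lesions such as non-melanoma skin cancer and in situ lesions are excluded.

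State that the event is dated at the earliest confirming procedure. Carry the same definition into the trial summary, the CT-confirmation wording of 4.1.4 and the case report form. Agree it across the GLOBAL BALLAD trials before the pooled analysis, because a UK-only change could itself create a difference between the contributing studies.

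The cost is a protocol amendment under 11.8, agreement among the collaborating trials, and a re-read of pathology and imaging reports already collected. Patients undergo no additional procedure.

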4.3.2 Secondary Endpoints

Overall survival: The patient's survival status is determined at each follow-up visit. After the mandated clinic visits survival status data will come from responsible cancer centres, cancer registries and national databases and include long-term passive follow-up data such as that collected through collaboration with the National Cancer Intelligence Network and the Office of National Statistics in the U.K.

Toxicity of chemotherapy: Toxicity will be assessed using CTCAE version 4.0. Only toxicities that are at least grade 2 will be recorded on the CRF

Quality of life: This is assessed using the EORTC QLQ-C30, EORTC QLQ-CR29 v2.1 and EQ-5D scales as per the schedule indicated in section 4.1.5

Health Economics: Assess the cost-effectiveness of 24 weeks adjuvant chemotherapy in comparison to observation alone; and assess the cost-effectiveness of 24 weeks adjuvant 5-FU/Capecitabine monotherapy compared to 5-FU/Capecitabine plus Oxaliplatin. Outcomes will be reported as incremental cost per DFS and incremental cost per QALY.

Establishment of a central tissue bank for patients with SBA – further details on this tissue bank can be found in section 4.2, Translational Research.

Establishment of a central repository of clinic-pathological, epidemiological and molecular profiling data of patients being treated with SBA in this trial.

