7.3 Analytical Plan

7.3.1 Primary Efficacy Analysis

The following approach will be taken for both trial questions (Adjuvant question and Oxaliplatin question). The primary frequentist analysis will be a conventional analysis of DFS using Cox regression techniques in the ITT population. Assuming this result is statistical significant at 20% 1-sided level of

Version 6: 16th July 2021 Page 57 of 87

statistical significance this result is then combined with the clinicians prior to determine a final posterior distribution.

Example: Assume the result of the trial was **just** statistically significant at 1-sided 20% level. The table below shows the 95% predictive intervals for DFS HR, based on trial data alone, a postulated clinician prior and the combined posterior distribution.

	Estimate of DFS	Lower limit of	Upper limit of 95%
	hazard ratio	95% predictive	predictive interval
		interval	
Trial data alone	0.88	0.65	1.18
Clinician prior	0.78	0.60	1.01
Combined posterior	0.82	0.68	1.00
distribution			

As can be seen when combined with the clinician prior, the 95% predictive interval excludes the possibility of any negative impact.

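### DFS is censored at the last date known alive, so time without disease assessment can count as disease-free; the rule should be last known alive and disease-free

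*Protocol*

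**What the plan says.** Section 4.3.1 defines DFS as time from randomisation to the first of relapse confirmed by imaging, a new primary confirmed by imaging and histology or cytology, or death from any cause. It then states: "Patients who experience none of these events are censored at the last date known to be alive". No other section adds that the patient must also be known to be free of disease on that date.

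Section 4.1.4 sets the disease assessments: "CT Chest Abdomen and Pelvis will be performed at approximately 12, 24 and 36 months post randomisation". Later scans follow clinical indication or site routine. Visits are six-monthly to 3 years, followed by "annual visits for up to 7 years post randomisation".

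Under overall survival, section 4.3.2 determines survival status at each follow-up visit and adds: "After the mandated clinic visits survival status data will come from responsible cancer centres, cancer registries and national databases". Footnote 10 to the schedules of assessments has quality-of-life forms posted home at 3 and 9 months, for observation patients only.

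Section 7.3.1 sets the analysis: "The primary frequentist analysis will be a conventional analysis of DFS using Cox regression techniques in the ITT population". The Bayesian steps in 7.1 and 7.3.1 follow only if that result is significant at the one-sided 20% level.

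**The concern.** Two of the three DFS event types can be recorded only if someone examines the patient for disease. Evidence that a patient is alive needs no such examination: it can come from a registry, a national database or a returned questionnaire. When that evidence is later than the last disease assessment, section 4.3.1 keeps the patient in the risk set as event-free through time in which a relapse could not have been seen. The relapse is then either never counted or counted only at death.

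Two quantities are exposed. The first is the level of DFS, which also feeds the prediction of OS from DFS (7.3.2) and the cost per DFS outcome (4.3.2). The second is the HR, if the gap between last assessment and last known alive differs between arms. The trial is open-label and the two arms of the adjuvant question have different contact patterns in the first 6 months, so a difference is possible there. It is less likely for the oxaliplatin question, where both arms receive chemotherapy.

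Because the rule is written in the protocol, an analysis plan would either inherit it or contradict it.

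**Working it through.** **1. The plan's own figures.** Inputs from sections 7.2 and 7.3.1: HR 0.775, one-sided alpha 0.20 (z = 0.8416), 1:1 allocation, 68 and 98 projected events. Power = Φ(|ln HR| × √d / 2 − 0.8416), with |ln 0.775| = 0.2549.

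- d = 68: 0.2549 × 4.123 − 0.8416 = 0.209, power 58.3% (plan: 58%).
- d = 98: 0.2549 × 4.950 − 0.8416 = 0.420, power 66.3% (plan: 66%).
- Required events with one non-binding futility look at half the events: 286.7 and 189.8 (plan: 287 and 190).

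The plan's figures reproduce. The required events do not depend on the censoring rule.

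**2. Simulation of the two rules.** 60,000 patients per scenario. From the plan: control 3-year DFS 45%, HR 0.775, 7 years' accrual plus 2 years' follow-up, protocol visit times. Assumed, because the documents give no figures: the annual rate of leaving clinic with vital status still known, 10% of DFS events being deaths without relapse, median post-relapse survival of 1.5 years, and relapse found at the next attended visit. Under the last-assessment rule, deaths counted only up to the time of leaving clinic.

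| Loss per year (observation / chemotherapy) | Control 3-year DFS: last known alive | Control 3-year DFS: last assessment | HR: last known alive | HR: last assessment |
|---|---|---|---|---|
| 0 / 0 | 44.9% | 44.0% | 0.785 | 0.786 |
| 5% / 5% | 47.1% | 43.6% | 0.776 | 0.774 |
| 10% / 10% | 49.2% | 43.2% | 0.780 | 0.778 |
| 20% / 20% | 52.2% | 42.2% | 0.789 | 0.779 |
| 10% / 3% | 48.9% | 43.3% | 0.824 | 0.773 |
| 3% / 10% | 46.2% | 43.8% | 0.740 | 0.787 |
| 20% / 5% | 52.3% | 42.0% | 0.861 | 0.761 |
| 5% / 20% | 47.0% | 43.4% | 0.708 | 0.790 |

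With equal loss of 5 to 20% per year, the written rule overstates a true 45% by about 2 to 7 points. The HR differs between rules by 0.002, 0.002 and 0.010. With unequal loss it differs by 0.051 (0.824 − 0.773), 0.047, 0.100 and 0.082, in the direction set by which arm loses more.

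**3. A milder illustration, with cumulative loss.** Here a stated percentage of patients leaves clinic over years 0 to 3, so these percentages are not comparable with the annual rates above. With 10% lost in each arm, 3-year DFS is about 1.3 points too high. With 20% lost on observation and 10% on chemotherapy, HR 0.775 reads as about 0.81. With |ln 0.81| = 0.2107, power at 68 events is Φ(0.2107 × 4.123 − 0.8416) = Φ(0.027), about 51%. With the loss reversed, the HR reads as about 0.75 and a null effect as about 0.96. The one-sided error is then Φ(0.0408 × 4.123 − 0.8416) = Φ(−0.673), about 25%.

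**4. Scale.** At 68 events significance needs an observed HR of at most exp(−0.8416 × 2 / √68) = 0.815. The standard error of ln HR is 2 / √68 = 0.24. A move from 0.775 to 0.81 is ln(0.81 / 0.775) = 0.044, about 0.2 standard errors.

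**The case against.** The strongest reply is that the gap may be small in this trial.

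- Section 4.3.2 describes passive tracing for overall survival, after the mandated visits, and those visits run to 7 years. Before then survival status is taken at the visit itself, so last known alive will often be the last attended visit.
- Patients who stop treatment stay on the visit schedule (3.7.1). For those who withdraw altogether, section 3.7.2 says: "Once a patient has withdrawn from the trial no further data will be collected on that patient". They add no later alive date.
- From 9 months both arms share one follow-up schedule (4.1.3).
- Deaths found by tracing still count as events, so part of what is missed is recovered late.
- With no loss the written rule was closer to the true 45% (44.9% against 44.0%).

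Most of this stands, and it limits the size. It does not remove the fault: nothing in the protocol rules out tracing before year 7 or ties the DFS censoring date to an assessment.

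A reader might infer more than the documents support:

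- *That DFS is overstated in every case.* This needs patients who leave clinic and are still known alive.
- *That the HR is biased, or that the error rate is 25%.* Those figures rest on unequal loss that was assumed.
- *That the direction of any bias cannot be known.* Missed assessments can be tabulated by arm.
- *That last-assessment censoring is free of bias.* Censoring survivors back to their last visit while counting deaths after it pulled DFS down to between 42.2% and 44.0% in the no-loss and equal-loss scenarios.

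**Conclusion.** The censoring rule in section 4.3.1 is wrong as written for DFS. It belongs to overall survival and credits unassessed time as disease-free. The size cannot be fixed from the documents, because they give no rate for patients who leave clinic follow-up while still known alive. The effect on the DFS level ranges from negligible with no loss to about 2 to 7 points at assumed equal losses of 5 to 20% per year. The HR is little affected by equal loss (about 0.01 or less) and can move either way under unequal loss. The figures of HR 0.81 and 51% power only illustrate an assumed 20% versus 10% loss.

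The HR concern applies mainly to observation versus chemotherapy and less to the oxaliplatin question. The point is worth correcting before analysis because it defines the primary endpoint, and the primary result decides whether the Bayesian steps are carried out.

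**What to change.** Replace the sentence in section 4.3.1 with: *Patients with none of these events are censored at the last assessment (clinic visit or imaging) at which they were known to be alive and free of relapse and new primary.* In addition:

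- Keep last date known alive for overall survival only.
- State how a death after a long gap without disease assessment enters DFS. Without this the new sentence is incomplete, for the reason given in the last item under the objection.
- Apply the same rule to every dataset pooled in GLOBAL BALLAD.
- Keep the present rule as a sensitivity analysis and tabulate loss to disease assessment by arm.

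The cost is one sentence, a small change to the derivation and slightly shorter DFS follow-up. The follow-up forms are not shown, so confirm that they record the assessment date. The required number of events is unchanged, but fewer may be observed if loss is heavy and deaths after leaving clinic are not counted: at 10% per year in both arms, 53.5% of simulated patients had an event, against 62.8% under the present rule. Because a clinic visit counts as an assessment, the new sentence does not make up for the absence of mandated CT after 36 months.
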